### **2.1 STUDY RATIONALE**

Based on the data from in vitro studies of RO7049389 there is a possibility of an organic anion-transporting polypeptide (OATP)-mediated interaction between RO7049389 and OATP1B1 substrates. In vitro, RO7049389 inhibits OATP1B1 mediated transport with a half maximal inhibitory concentration (IC50) of 3 µM (1796 ng/mL). This IC50 is predicted to be lower than RO7049389 exposures at the expected efficacious dose. The 3-hydroxy-3-methyl-glutaryl-coenzyme A (HMG-CoA) reductase inhibitors or 'statins', a class of cholesterol-lowering drugs, are known substrates for OATP1B1. In future clinical trials, a statin may be a concomitant medication with RO7049389. Therefore, it will be important to understand the effect, if any, of RO7049389 on the pharmacokinetics (PK) of such an OATP1B1 substrate.

The rationale for the study design is provided in Section [4.2](#).

### **2.2 BACKGROUND**

#### **2.2.1 Background on Hepatitis B Virus**

Hepatitis B virus (HBV) infection is a major cause of both acute hepatitis and chronic liver diseases, including cirrhosis and hepatocellular carcinoma. Approximately two billion people worldwide have serological evidence of past or present HBV infection. An estimated 686 000 people are estimated to die each year due to the acute or chronic consequences of hepatitis B ([WHO 2016](#)).

Currently, there are two classes of drugs available for the treatment of chronic hepatitis B (CHB): subcutaneously administered interferon (IFN) preparations and orally administered nucleos(t)ide analogues (NUCs). Although both types of treatment can induce the loss of HBV envelope antigen with development of anti-HBeAg antibody (serological response), the suppression of HBV DNA to an undetectable level by sensitive polymerase chain reaction (PCR) methods (virological response), and are able to normalize liver transaminases levels (biochemical response), neither treatment achieves a high rate of clinical cure. Hepatitis B surface antigen (HBsAg) loss, with various therapies (NUCs or INF) only occurs in approximately 3% after one year of treatment. HBsAg loss rates increase to 9% at 3 years and 12% at 5 years following PEG-IFN-2a therapy ([EASL 2017](#)). In clinical studies, the combination of NUCs with PEG-IFN has not been proven superior to PEG-IFN alone for the most prevalent genotypes in the world, i.e., B, C and D ([Marcellin 2016](#)). In addition, IFN-based therapies are associated with many side-effects, while NUCs frequently require prolonged or possibly life-long therapy, and some are associated with a high risk of viral resistance.

## 2.2.2 Background on RO7049389

RO7049389 is an inhibitor of HBV capsid assembly and belongs to the well-studied class of heteroaryldihydropyrimidine (HAP) compounds. This class of compounds induces formation of abnormal HBV core protein aggregates, which are subsequently recognized and depleted. Depleting functional core protein results in interruption of viral assembly and inhibition HBV replication.

[REDACTED]

The entry-in-human (EIH) study, YP39364, with RO7049389 is ongoing. This is a randomized, Sponsor-open, Investigator-blinded, subject-blinded, placebo-controlled study to investigate the safety, tolerability, PK and pharmacodynamics (PD) of RO7049389 in: (1) single- (with or without food) and multiple- (with midazolam) ascending doses in healthy volunteers (HVs); (2) patients chronically infected with hepatitis B virus.

[REDACTED]

[REDACTED]

A detailed description of the chemistry, pharmacology, efficacy and safety of RO7049389 is provided in the [RO7049389 Investigator's Brochure](#).

### **2.2.3 Background on Pitavastatin**

Pitavastatin is an approved HMG-CoA reductase inhibitor (i.e., statin), used in the treatment of hypercholesterolemia. Statins have been shown to reduce cardiovascular morbidity and mortality, and their efficacy and safety for the primary and secondary prevention of cardiovascular events have been demonstrated in a large number of clinical trials.

Dose-proportional increases in pitavastatin  $C_{max}$  and  $AUC_{inf}$  were observed following daily administration ranging from 1 to 24 mg. Given with a high-fat and high-calorie meal,  $C_{max}$  decreased by 43% but the AUC did not decrease significantly. The mean plasma elimination half-life ( $t_{1/2}$ ) is approximately 12 hours (LIVALO® U.S. Package Insert). Per the transporter expressing HEK293 cells and human cryopreserved hepatocytes, the OATP1B1 and OATP1B3 transporter account for almost all the observed pitavastatin uptake clearance into human hepatocytes and OATP1B1 accounts for about 90% of the clearance (Hirano et al 2004). Pitavastatin has been reported to be sensitive to OATP1B inhibition (Prueksaritanont et al 2014).

Pitavastatin was generally well-tolerated in clinical trials of up to 60-week duration, with a tolerability profile broadly similar to that of atorvastatin and simvastatin (Duggan 2012). The adverse-events (AE) profile of pitavastatin compares favorably with those of other available statins. Reported AEs of pitavastatin included gastrointestinal symptoms (0.7%–2.2%), myopathies (0.3%–1.1%), and elevated hepatic enzyme concentrations (0.0%–8.8%; Yee et al 2011).

A detailed description of the chemistry, pharmacology, efficacy and safety of pitavastatin is provided in the pitavastatin package insert hours (LIVALO® U.S. Package Insert).

### **2.3 BENEFIT/RISK ASSESSMENT**

This study has the principal aim of characterizing the drug-drug interaction between RO7049389 and an OATP substrate, the cholesterol-lowering drug pitavastatin, a representative of the statin class, in a population of healthy volunteers. There will be no therapeutic benefit for the healthy volunteers participating in the study. However, assessment of the influence of RO7049389 on the safety and PK of pitavastatin brings valuable information for the development of RO7049389. The target population could be exposed to statins or other OATP1B1 substrates, therefore, the results from the study will provide essential information to guide dosing of statins when co-administered with RO7049389.

The risks for the individual participant due to exposure to RO7049389 and/or pitavastatin or study-related procedures are considered acceptable or low in this study.

[REDACTED]

The risks

associated with two administrations of 2 mg single dose of pitavastatin in this study are also considered acceptable or low due to extensive clinical experience with pitavastatin at doses up to 24 mg and over much longer treatment durations, up to 60 weeks (Duggan 2012). In addition, careful safety monitoring of all critical safety parameters will be performed throughout this study and there will be close monitoring of all participants during dosing and in-clinic stay.

More detailed information about the known and expected benefits in the context of potential risks and reasonably expected adverse events of RO7049389 is provided in the [RO7049389 Investigator's Brochure](#).

### 3. OBJECTIVES AND ENDPOINTS

The objectives and corresponding endpoints are provided in [Table 3](#).

**Table 3 Objectives and Endpoints**

Objectives	Endpoints
Primary	

 
To determine the effect of multiple-doses of RO7049389 on the single-dose pharmacokinetics (PK) of pitavastatin in healthy participants.
 
	
 
Primary PK parameters of pitavastatin: <math>C_{max}</math>, and <math>AUC_{0-inf}</math>
 
Secondary PK parameters of pitavastatin: <math>t_{max}</math>, CL/F, V/F and <math>t_{1/2}</math>.
 
Other parameters may be calculated if considered appropriate.
 

Secondary	

 
To evaluate the safety and tolerability of the single-dose pitavastatin alone and in combination with multiple-doses of RO7049389 in healthy participants.
 
To explore the effect of the single-dose of pitavastatin on steady-state PK of RO7049389 in healthy participants.
 
To determine the effect of multiple-doses of RO7049389 on the single-dose PK of pitavastatin lactone in healthy participants (if applicable).
 
	
 
Incidence and severity of adverse events.
 
Incidence of laboratory abnormalities based on hematology, clinical chemistry, coagulation, lipids, and urinalysis test results.
 
ECGs.
 
Vital signs including blood pressure (BP), pulse rate and body temperature.
 
Primary PK parameters of RO7049389 and its metabolites (RO7121986, RO7255420 and RO7255422): <math>C_{max}</math>, and <math>AUC_{tau}</math>.
 
PK parameters of pitavastatin lactone: <math>C_{max}</math>, and <math>AUC_{0-inf}</math>.
 
The AUC ratio of pitavastatin lactone/pitavastatin.
 

Exploratory	

 
To evaluate the effect of multiple-doses of RO7049389 on OATP activity as assessed by plasma and urine coproporphyrins (CP-I and CP-III).
 
	
 
Coproporphyrins (CP-I and CP-III) AUC in plasma and amount excreted in urine.
 

## **4. STUDY DESIGN**

### **4.1 OVERALL DESIGN**

This is an open-label, fixed sequence, two-period study designed to evaluate the drug-drug interaction between RO7049389 and pitavastatin and the safety and tolerability of single-dose pitavastatin alone and in combination with multiple-doses of RO7049389 in healthy participants.

An overview of the study design is provided in Section [1.2](#).

#### **4.1.1 Length of the Study**

The total duration of the study for each participant will be about 12 weeks divided as follows:

- Screening: Up to 28 days.
- Period 1:
  - In clinic period: Days -1 to 4.
  - Treatment period: Day 1
- Wash-out Period: Defined as from Period 1 Day 1 to Period 2 Day 1 and lasts at least 7 days but not more than 21 days
- Period 2:
  - In clinic period: Days -1 to 7
  - Treatment period: Days 1 to 6
- Safety follow-up:
  - Period 2 Day 13
  - Period 2 Day 34 (Telephone call)

The participant has the option to stay in clinic during the whole Period 1 and wash-out period if agreed by Sponsor and the Investigator.

### **4.2 SCIENTIFIC RATIONALE FOR STUDY DESIGN**

The study rationale is provided in Section [2.1](#).

This is an open-label, fixed sequence, two-period study.

The primary objective of this study is to determine the effect of multiple-doses of RO7049389 on the single-dose PK of pitavastatin in healthy participants. As PK measurements are objectively analysed an open-label study design has been chosen. To minimize the number of participants needed and reduce inter-subject variability, this study will follow a two-period instead of parallel design. The duration of both washout and drug administration periods was established on the basis of the known

pharmacokinetic profiles of both RO7049389 and pitavastatin. The half-life [REDACTED] of RO7049389 was used to calculate the likely time needed for steady state and that of pitavastatin was used to calculate the duration needed to capture its entire elimination phase. To ensure the full potential for an interaction is realized (maximal inhibition of OATP), pitavastatin will be co-administered with RO7049389 while the latter is in steady state. Administration of RO7049389 will be continued throughout the whole elimination phase of pitavastatin. Accordingly, a fixed sequence design has been chosen for logistical reasons.

#### **4.2.1 Rationale for Study Population**

Male and female healthy volunteers have been selected as the study population for this study as the absence of confounding disease processes is expected to lead to a clear and consistent assessment of drug disposition and biological activity. This population is unlikely to require concomitant treatments that could interfere with the study drug and safety evaluations.

#### **4.2.2 Rationale for Biomarker Assessments**

Coproporphyrins (CP-I and CP-III) AUC ratios in plasma and amount excreted in urine ratios will be measured as endogenous markers for hepatic OATP1B1 inhibition. CP-I and III are porphyrin metabolites arising from heme synthesis and eliminated through bile and urine. CP-I and CP-III in plasma and the amount excreted in urine are reported to be substrates of OATP1B1 and OATP1B3 (Yurong Lai et al., 2016).

Correlation between pitavastatin clearance and endogenous substances will be explored in this study. If OATP1B1 activity needs be monitored for future RO7049389 clinical studies, the Coproporphyrins (CP-I and CP-III) AUC in plasma and/or amount excreted in urine, instead of pitavastatin, can be conveniently employed in such studies.

[REDACTED]

[REDACTED]

[REDACTED]

[REDACTED]

[REDACTED]

RO7049389 will be administered for 6 days with concurrent administration on Day 4 with pitavastatin and any possible OATP inhibition is at its maximum at steady state.

Pitavastatin was approved at dose range of 1 mg to 4 mg once daily. As potential OATP1B1 mediated exposure increase cannot be excluded when given in combination with RO7049389, a single dose of 2 mg of pitavastatin was chosen in this study considering the demonstrated safety and linear pharmacokinetics PK across a dose range of 1 mg to 24 mg following single dose.

The dosing periods selected for this study have been chosen to ensure that steady state will have been reached for RO7049389, and any possible significant drug-drug interaction will be detected, whilst minimizing exposure to any drug to the shortest period necessary.

Further details are provided in the [RO7049380 Investigator's Brochure](#)

#### **4.4 END OF STUDY DEFINITION**

A participant is considered to have completed the study if he/she has completed all parts of the study including the last scheduled procedure shown in the Schedule of Activities.

The end of the study is defined as the date when the last participant last observation (LPLO) occurs. LPLO is expected to occur 28 days after the last dose of RO7049389 is administered.

## **5. STUDY POPULATION**

The study population rationale is provided in Section 4.2.1.

The participants of this study will be healthy male and female volunteers of 18 to 60 years of age (inclusive). The study will enroll up to a total of 18 participants to obtain 16 evaluable participants.

Participants who drop out of the study, or who are withdrawn, for non-safety reasons may be replaced. Participants who withdraw from the study due to poor tolerability or due to study drugs (RO7049389 or pitavastatin) related adverse events will not be replaced.

Prospective approval of protocol deviations from recruitment and enrollment criteria, also known as protocol waivers or exemptions, is not permitted.

### **5.1 INCLUSION CRITERIA**

Participants will be eligible to be included in the study only if all of the following criteria apply:

#### **Informed Consent**

1. Able and willing to provide written informed consent and to comply with the study protocol according to ICH and local regulations.

#### **Age**

2. 18 to 60 years of age, inclusive, at the time of signing the informed consent.

#### **Type of Participants and Characteristics**

3. Healthy, as judged by the Investigator.

Healthy status is defined by absence of evidence of any active or chronic disease following a detailed medical and surgical history, a complete physical examination including vital signs, 12-lead ECG, and based on the laboratory safety test results at screening and Day -1.

4. Body mass index (BMI) between 18 to 30 kg/m^2 (inclusive) at screening.
5. Male and female participants

The reliability of sexual abstinence should be evaluated in relation to the duration of the clinical trial and the preferred and usual lifestyle of the patient. Periodic

abstinence (e.g., calendar, ovulation, symptothermal, or post-ovulation methods) and withdrawal are not acceptable methods of contraception.

a) Female Participants

Female participants must be either surgically sterile (by means of hysterectomy and/or bilateral oophorectomy and/or tubal ligation) or post-menopausal for at least one year (defined as amenorrhea  $\geq$  12 consecutive months without another cause, and confirmed by follicle-stimulating hormone (FSH) level. Participants must not be pregnant or lactating.

b) Male Participants

With female partners who are not pregnant or lactating.

With agreement to remain abstinent (refrain from heterosexual intercourse) or use contraceptive measures, and agreement to refrain from donating sperm, as defined below:

With female partners of childbearing potential, men must remain abstinent or use a condom during the treatment period and for at least 28 days after the last dose of study drug to avoid exposing the embryo. Men must refrain from donating sperm during this same period.

## 5.2 EXCLUSION CRITERIA

Participants will be excluded from the study if any of the following criteria apply:

### Medical Conditions

1. Have a history or symptoms of any clinically significant cardiovascular, respiratory, hepatic, renal, gastrointestinal, endocrine, hematological, oncologic or neurological disorders capable of significantly altering the absorption, metabolism, or elimination of drugs; of constituting a risk when taking the study treatment; or of interfering with the interpretation of data.
2. Confirmed (based on the average of 3 separate resting BP measurements in a supine position, after at least 5 minutes rest) systolic BP greater than 140 or less than 90 mmHg, and diastolic BP greater than 90 or less than 50 mmHg at screening and Day -1.
3. Personal history or family history of congenital long QT syndrome and/or cardiac sudden death.
4. History of Gilbert's syndrome.
5. Participants who have had significant acute infection, e.g., influenza, local infection, acute gastrointestinal symptoms or any other clinically significant illness within two weeks of dose administration.

6. Any confirmed significant allergic reactions (urticaria or anaphylaxis) against any drug, or multiple drug allergies (non-active hay fever is acceptable).
7. Any clinically significant concomitant diseases or condition that could interfere with, or treatment of which might interfere with, the conduct of the study, or that would, in the opinion of the Investigator, pose an unacceptable risk to the participant in this study.

### **Prior/Concomitant Therapy**

8. Taking any herbal medications or substances (e.g., tea) or supplements (including vitamins), or traditional Chinese medicines (TCM) or over-the-counter (OTC) medications within 14 days of first dosing or within 5 times the elimination half-life of the medication prior to first dosing, whichever is longer.

Exceptions include medications listed under Permitted Therapy and those made on a case-by-case basis following discussion and agreement between the Investigator and the Sponsor.

9. History of having received any systemic anti-neoplastic (including radiation) or immune-modulatory treatment (including systemic oral or inhaled corticosteroids)  $\leq$  6 months prior to the first dose of study drug or the expectation that such treatment will be needed at any time during the study.

### **Prior/Concurrent Clinical Trial Experience**

10. Are currently enrolled in or have participated in any other clinical study involving an investigational product or in any other type of medical research within the last 30 days or 5 half lives (whichever is longer).
11. Donation or loss of blood or blood products in excess of 500 mL within 3 months of screening.

### **Diagnostic Assessments**

12. Positive test for drugs of abuse (including recreational drugs) and/or positive alcohol test and/or positive cotinine test at screening and on Day -1.
13. Clinically relevant ECG abnormalities on screening or Day -1 ECG based upon the average of three ECGs, e.g.:
  - a. QTcF  $>$  450 msec or  $<$  300 msec.
  - b. Notable resting bradycardia (HR  $<$  45 bpm), or HR  $>$  90 bpm.
  - c. Evidence of atrial fibrillation, atrial flutter, complete bundle branch block, Wolf-Parkinson-White Syndrome, or cardiac pacemaker.
14. ECG with QRS and/or T-wave judged by the Investigator to be unfavorable for a consistently accurate QT measurement (e.g., neuromuscular artifact that cannot be readily eliminated, arrhythmias, indistinct QRS onset, low amplitude T-wave, merged T- and U-waves, prominent U- waves).

15. Creatinine Clearance (CrCl)  $\leq$  70 mL/min at screening or on Day -1 (may be repeated for confirmation).
16. Positive test at screening of any of the following: Hepatitis A virus (HAV IgM Ab), hepatitis B virus (HBsAg or HBcAb), , hepatitis C virus (HCV RNA or HCV Ab) or human immunodeficiency virus (HIV-1 and HIV-2 Ab).
17. Any other clinically significant abnormalities in laboratory test results at screening or on Day -1. In the case of uncertain or questionable results, tests performed during screening may be repeated once prior to enrollment to confirm eligibility unless deemed not clinically significant by the Investigator.

### **Other Exclusions**

18. History of alcohol consumption exceeding 2 standard drinks per day on average (1 standard drink= 10 grams of alcohol) and/or drug abuse within 12 months of screening.
19. Use of > 5 cigarettes or equivalent nicotine-containing product per day prior to screening.
20. Participants under judicial supervision, guardianship or curatorship.
21. Medical or social conditions that would potentially interfere with the participant's ability to comply with the study visit schedule or the study assessments.
22. Sensitivity to any of the study treatments, or excipients thereof, or drug or other allergy that, in the opinion of the Investigator or Medical Monitor, contraindicates the participation in the study.

## **5.3 LIFESTYLE CONSIDERATIONS**

### **5.3.1 Meals and Dietary Restrictions**

Food and water will be restricted as follows:

- Any nutrients known to modulate activity of CYP enzymes or OATP transporters (e.g., grapefruit-, apple-, or Seville orange-containing products) will be prohibited within 3 days before Period 2 Day -1 through the last dose of RO7049389, which is on Period 2 Day 6.
- Approximately 240 mL of still water at room temperature will be provided for each dose. No water is allowed until 2 hours after each dose, after which time, water is allowed ad libitum.

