**Table 2 Schedule of Activities – Detailed Table (cont.)**

- a. Vital signs include triplicate measurements of blood pressure and pulse rate and single assessment of body temperature after the participant has been in a supine position for at least 5 minutes.
- b. 12-lead ECGs will be obtained in triplicate after the participant has been in a supine position for at least 10 minutes. Automated ECG intervals (PR [PQ], QRS, QT, QTcF, RR) and HR will be captured or calculated, and the changes in T-wave and U-wave morphology will be documented.
- c. Urine samples will be collected at -7-0 hours pre-dose (Day -1 of Period 1), 0-7 and 7-24 hours post-dose (Day 1 of Period 1), 0-7 and 7-24 hours post-dose (Day 4 of Period 2).

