### **5.3.2 Caffeine, Alcohol, and Tobacco**

Caffeine, alcohol, and tobacco will be restricted as follows:

- During each period, participants must abstain from ingesting caffeine- or xanthine-containing products (e.g., coffee, tea, cola drinks, and chocolate) for 48 hours before the start of dosing until after collection of the final PK sample.

- Alcohol must not be consumed from 48 hours before screening, 48 hours before admission until completion of follow-up visit on Day 13 of Period 2.
- Participants who use tobacco products will be instructed that use of nicotine-containing products (including nicotine patches) will not be allowed from screening until after the final follow-up visit.

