### **5.3.3 Activity**

Participants must abstain from strenuous exercise for at least 72 hours before each blood collection for clinical laboratory tests. Participants may participate in light recreational activities during study (e.g., watching television, reading).

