**Table 4 Summary of Treatments Administered**

Study Treatment Name:	RO7049389	Pitavastatin
Dosage Formulation:	Tablet	Tablet
Unit Dose Strength(s):	200 mg	2 mg
Dose:	800 mg BID	2 mg
Route of Administration:	Oral	Oral
Dosing Instructions:	4 tablets to be taken, with food	1 tablet to be taken, with food
Packaging and Labeling:	Study treatment will be provided in labeled bottles.	
Manufacturer	F. Hoffmann-La Roche Ltd	Kowa

Study treatments will be administered orally to the participants by investigational staff for all dosing with still water at room temperature.

Pitavastatin will be administered orally to participants by investigational staff in the morning on Day 1 of Period 1 and Day 4 of Period 2. Thirty minutes before the administration, a standard meal will be served to participants, which should be consumed within thirty minutes. RO7049389 will be administered orally to participants by investigational staff from Day 1 to Day 6 of Period 2 twice daily. The first daily dosing will be administered in the morning and the second daily dose will be in the evening, with approximately 12 hours interval. In the morning of Day 4 of Period 2, pitavastatin will be administered together with RO7049389.

For RO7049389, please see the [RO7049389 Investigator's Brochure](#) for more details.

For pitavastatin, see the local prescribing information for more details.

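### The ban on CYP/OATP-modulating foods is written for Period 2 only, so no food rule precedes the Period 1 pitavastatin reference dose or the coproporphyrin baseline

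*Combined protocol and SAP*

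**What the plan says.** Section 5.3.1 holds the only rule on ordinary foods that modulate CYP enzymes or OATP transporters. It gives grapefruit, apple and Seville orange products as examples. These foods "will be prohibited within 3 days before Period 2 Day -1 through the last dose of RO7049389", which the section dates to Period 2 Day 6. Nothing equivalent is written for Period 1.

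The surrounding rules are these:

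- **Confinement (Section 4.1.1).** For Period 1 the entry is "In clinic period: Days -1 to 4"; Period 2 also starts in clinic on Day -1 and runs to Day 7. In addition, "The participant has the option to stay in clinic during the whole Period 1 and wash-out period", if the sponsor and investigator agree.
- **Meals (Section 6.1).** On dosing with pitavastatin, "Thirty minutes before the administration, a standard meal will be served to participants, which should be consumed within thirty minutes". The content of that meal, and of other clinic meals, is not described.
- **Caffeine (Section 5.3.2).** "During each period, participants must abstain from ingesting caffeine- or xanthine-containing products", starting 48 hours before dosing.
- **Alcohol (Section 5.3.2).** "Alcohol must not be consumed from 48 hours before screening, 48 hours before admission", continuing to the follow-up visit.
- **Prior and concomitant products (Exclusion 8, Section 6.5.2).** Herbal substances, supplements and medicines are restricted for 14 days or five half-lives before first dosing, whichever is longer. First dosing is the Period 1 pitavastatin dose.

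Section 9.4.3 compares pitavastatin with and without RO7049389, with pitavastatin alone (Period 1) as the reference, in an ANOVA with factors for RO7049389 and participant. Sections 8.8 and 9.4.5 form coproporphyrin ratios of after to before RO7049389. Section 6.3.1 confirms that the sequence is fixed.

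**The concern.** The primary result is a ratio whose denominator comes from Period 1, and the coproporphyrin result is an after/before ratio with the same baseline period. Each participant is their own control, so the comparison relies on the two periods differing only in RO7049389. Here they also differ in a written dietary condition, and the protocol itself describes the restricted foods as able to modulate OATP transporters, the class of transporter under study.

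Treatment and period coincide in a fixed sequence, so no term in the ANOVA could absorb such a difference. That is an accepted limit of the design and not a second fault. It does mean that matched conditions are the protection available, and that a mismatch cannot be repaired once Period 1 has been dosed. If diet moved exposure in one direction before the reference profile, the ratio would carry it. If it moved exposure in some participants either way, the within-participant variance would grow.

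**Working it through.** **Inputs.** Ban start: 3 days before Period 2 Day -1 (Section 5.3.1). Washout *w*, from Period 1 Day 1 to Period 2 Day 1: 7 to 21 days (Section 4.1.1). Pitavastatin doses: Period 1 Day 1 and Period 2 Day 4 (Section 6.1). Sampling: Tables 1 and 2. The schedule has no Day 0.

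**When the ban starts.** Period 2 Day 1 falls on Period 1 Day 1 + *w*. Period 2 Day -1 is the day before, Period 1 Day *w*. The ban starts 3 days earlier, on Period 1 Day *w* - 3.

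| Washout *w* | Ban starts on Period 1 Day |
|---|---|
| 7 | 4 |
| 8 | 5 |
| 14 | 11 |
| 21 | 18 |

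The earliest possible start is 3 days after the reference dose.

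**What is collected before it.**

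- Pitavastatin in Period 1: 12 (Day 1) + 2 (Day 2) + 1 (Day 3) + 1 (Day 4) = 16 samples. The 72-hour sample on Day 4 can fall inside the ban only when *w* = 7. So 15 samples (*w* = 7) or 16 (*w* of 8 or more) come before it.
- Coproporphyrin baseline: plasma 10 + 1 = 11; urine, one pre-dose and two post-dose intervals = 3. All finish by 24 hours (Day 2), so all 14 come before the ban.

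**Restricted days before each pitavastatin dose.** Test dose: Period 2 Days -4, -3, -2, -1, 1, 2, 3 = 7. Reference dose: 0.

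**Which Period 1 days are open.** The days before Day -1 are always outside the clinic and carry no food rule. Days -1 to 4 are in clinic, but no section says that clinic meals exclude these foods, so they may be open too (except Day 4 when *w* = 7). A participant who stays in clinic through the washout spends the 3 lead-in days in clinic before Period 2; no such option exists before Period 1.

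**Size of any effect.** It cannot be obtained from the documents. The following is an illustration only, with assumed mean shifts in reference exposure. It uses n = 16 and the 30% CV of Section 9.2, log variance ln(1.09) = 0.0862, and t(0.95, 15) = 1.753. Coverage is the probability that a noncentral t variable with 15 df and noncentrality ln(1 + shift)/SE lies within ±1.753.

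| Reading of the 30% CV | SE of log ratio | Half-width of 90% CI at that variance | Shift at which coverage falls to 89% | to 85% |
|---|---|---|---|---|
| CV of a single observation | sqrt(2 × 0.0862/16) = 0.1038 | 0.182 | 2.7% | 6.1% |
| CV of the within-participant difference | sqrt(0.0862/16) = 0.0734 | 0.129 | 1.9% | 4.3% |

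Shifts are averages over all 16 participants; if only some are affected, the effect in them must be larger. With no net direction there is no bias. Under the first reading (log-difference variance 2 × 0.0862 = 0.1724), if 25% of participants were affected by a factor of 0.8 or 1/0.8, the added variance would be 0.25 × ln(0.8)² = 0.0124. That is 7.2% of 0.1724, or 3.5% on the half-width.

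**The case against.** Several points can fairly be made for the plan as written.

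- **Other rules cover part of the ground.** Exclusion 8 and Section 6.5.2 already restrict herbal substances, supplements and medicines before the reference dose, for longer than 3 days. This stands, and it narrows the gap to ordinary foods, which neither rule names.
- **Dose-time conditions are largely matched.** Both pitavastatin doses are given by staff, in clinic, after a standard meal, with admission on Day -1 in both periods. This stands. It does not reach the days before Period 1 admission, and the meal's content is unstated.
- **The mechanism is not shown.** Section 5.3.1 speaks of CYP enzymes or OATP transporters in general. The pathway under test is OATP1B1, and no section says that any listed food affects OATP1B1, pitavastatin or coproporphyrins. This stands, and it is why no bias is claimed.
- **The comparison with neighbouring rules is thin.** The water rule is a dosing instruction, the exercise rule ("Participants must abstain from strenuous exercise for at least 72 hours before each blood collection") concerns clinical laboratory tests, and alcohol and nicotine are near-continuous bans. Only the caffeine rule is a PK-type restriction written for each period. So the contrast suggests an oversight but does not prove one.
- **A reason may exist in redacted text.** Parts of the RO7049389 background and dose rationale are blacked out, so a deliberate link to RO7049389 dosing cannot be excluded. The wording and dates of the food rule are nevertheless fully visible.

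A reader might also infer that the mismatch is confined to, or mainly, the 3 pre-admission days. That would need Period 1 clinic meals to be free of these foods, which the documents do not say.

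**Conclusion.** The point holds as an unmatched condition in the written plan. For every permitted washout, the food rule starts after the reference dose and after the whole coproporphyrin baseline, with 0 restricted days before the reference dose against 7 before the test dose. This rests only on the text and the day count, and confidence in it is high.

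The consequence is much less certain. A reader might infer that the pitavastatin ratio or the coproporphyrin ratio is biased. The documents do not support that: they give no size, direction, persistence or frequency of intake for a food effect, and do not link the listed foods to OATP1B1. The effect may be nil. The coverage thresholds are not evidence of harm; they rest on assumed shifts and change with how the 30% CV is read. What remains is an avoidable risk of bias or added variance that the analysis could not remove, and a cheap improvement worth considering.

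**What to change.** Add to Section 5.3.1 that the same foods are prohibited from 3 days before Period 1 Day -1 through the last Period 1 PK sample on Day 4, including in clinic meals, and keep the Period 2 window as it stands.

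**Cost.** One sentence. Participants avoid a few foods on Period 1 Days -4 to -1 and 1 to 4, which is 8 more days, or 7 at the 7-day washout because Day 4 is already covered. Three of these days (Days -4 to -2) are outside the clinic. No visits or samples are added.

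**What it leaves.** The pre-admission and in-clinic rules would then match, but the day count would not: 4 restricted days before the reference dose against 7 before the test dose. The extra 3 are in-clinic days (Period 2 Days 1 to 3). If an equal lead-in is wanted, the ban can start 7 days before Period 1 Day 1, at 11 more days (10 at the 7-day washout), 6 of them outside the clinic.

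If the rule is meant for Period 2 only, the protocol should give the reason and confirm that Period 1 clinic meals exclude these foods.
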